Project Objectives. This study will determine the impact of HWA usage on mobility in the home and community in individuals with PD. It will also examine feasibility and safety of HWA usage in the PD population. **As mobility limitations are highly associated with poor quality of life in people with PD,¹⁹⁻²¹ any benefits of HWA usage to improve mobility are likely to positively impact the health and well-being of individuals with PD.** **Specific Aim 1:** Determine the short-term impact of mechanical gait assistance on efficiency and ease of walking in individuals with PD. With disease progression, individuals with PD develop gait impairments (e.g., slower gait velocity, shorter step lengths, increased step-to-step variability, and freezing of gait), that interfere with their abilities to perform daily living tasks and participate in work, home, and social activities and predispose them to falls.²² *We hypothesize that wearing the HWA device will improve gait efficiency, gait parameters, and perceived ease of walking in individuals with PD compared to unassisted walking over a one session period.* Positive findings of immediate improved walking efficiency and perceived ease of walking will suggest that HWA usage can ameliorate gait impairments in individuals with PD, and thereby possibly allow them to more easily perform daily tasks, participate in work, home, and social activities, and reduce their fall risk. **Specific Aim 2:** Determine the effect of long-term HWA device usage on the ease and ability to walk unassisted in the home and community in individuals with PD. Angular sensors embedded in the HWA monitor the cadence, angular velocity, and degree of hip extension and flexion of the device user.¹⁴ When the user initiates walking, the HWA automatically adjusts leg movements to reach target walk ratios (step length/cadence) by increasing the amount of hip flexion and/or extension using power supplied by the device. Thus, the HWA applies continuous, step-by-step cueing to individuals with PD to take bigger and more symmetrical steps, thereby producing a faster and more efficient walking pattern. By wearing the HWA device over an extended period of time, individuals with PD will repetitively practice walking with a more “normal” gait pattern, possibly driving neuroplastic changes that will translate to improve unassisted walking. *We hypothesize that an 8-week intervention of HWA device usage will improve gait efficiency, gait parameters, perceived ease of walking, self-confidence, and daily physical activity in the home and community in individuals with PD with and without the use of the device.* Positive findings would justify larger clinical trials to determine the efficacy of HWA device usage to encourage adherence to rehabilitation programs and to promote maintenance of an active lifestyle in individuals with PD.

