
METHODS

Participants: Adults aged 50-80 (n=46) who ambulate without assistance (Hoehn & Yahr stages 1-3) with diagnosed idiopathic PD and on stable doses of Parkinson’s medications for at least 4 weeks prior to the study will be recruited from the Ohio State Movement Disorders Clinic and community support groups. Exclusion criteria will be: presence of other significant cardiac, neurological or orthopedic problems that affect gait, weight more than 220 pounds and height greater than 6’8”, electronic medical devices embedded in the body, participating in any physical therapy, and inability to understand instructions

required by the study. **Study Design:** Proof-of-concept of the HWA device has already been established in prior single arm studies.¹⁴⁻¹⁸ This study will be a prospective Phase II randomized controlled trial to assess preliminary efficacy. **HWA Device:** The HWA device weighs 5.95 lbs and has two motors that run on a single rechargeable battery (Figure 2). The device is equipped with angle and current sensors to monitor hip joint angle and torque output respectively. The assist torque is transmitted to the user's thighs via thigh frames. A trained healthcare

professional, who operates the device, can remotely change assist settings through software that runs on a mobile device. Honda will provide the researchers with a minimum of 3 HWA devices of different sizes for use in this study. The HWA devices have points of adjustability at the Waist Frame and Thigh Frames (Figure 2), such that the devices can accommodate ~75% of adult, United States (US) body sizes. **Randomization:** After obtaining written informed consent, participants will be randomly assigned to 1 of 2 groups (Trained – HWA group, Untrained – usual care group). Randomization allocation will be 1:1 and stratified by Hoehn & Yahr stage. Each stratum randomization scheme will be generated in permuted blocks of varying size. These techniques will help to ensure a balance in the randomization among stage. The randomization scheme will be prepared, uploaded and overseen by the study's biostatisticians. Given the nature of the intervention proposed, participants will know the intervention to which they have been assigned. Therefore, it will only be possible to blind assessors in this study.

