Outcomes: Gait efficiency will be assessed with the six-minute walk test (6MWT),²⁵ gait parameters (i.e., velocity, stride length, swing time, double support, and their coefficients of variability) using GAITRite,²⁶ gait safety using counts of observed episodes of stumbles and/or loss of balance, and participants' perceived ease of walking as indicated on a visual analog scale (100 mm line with anchors "Not at all easy" on the left end and "Extremely easy" on the right end). The GAITRite System[®] (CIR systems, Inc.: Havertown PA) is a 4.88 m electronic walkway with sensors arranged in a gridlike pattern to capture footfall contacts. The application software (version 3.9) processes the raw data into footfall patterns and computes spatial and temporal parameters. Participants will walk at a normal, comfortable pace across the walkway for 4 trials. The first trial under each condition will be a practice trial and the data from the remaining three trials for each condition will be averaged. **Aim 2:** All individuals (n=46) will participate in this part of the study. **Intervention:** After undergoing the pre-assessment, participants randomized to the Trained group will be fitted with the HWA device in their home by a research physical therapist. They will be directed to walk with the device on and the therapist will adjust the settings until a safe gait pattern is obtained. The initial setting used will be the one that produced the safest walking at the pre-assessment. Adjustments will be made based on the response to this initial setting. Participants who achieve a safe gait pattern will receive physical therapist supervised home and community-based walking training wearing the HWA device 2 times per week for 45-60 minutes for 8 weeks. Training will consist of walking in and outside of the home while encouraging larger and more symmetrical steps with practice of activities (e.g., multi-directional stepping, turning, navigating around obstacles) that challenge the person's balance and motor control. Rest breaks will be allowed as needed. If the therapist is unable to adjust the HWA to provide a safe gait pattern, the session will be ended and the device removed. The Untrained group will continue their usual daily activities including any exercise regimen that they typically perform. However, they will be asked not to start any new exercise program during the study period.

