Outcomes: All assessments will be performed within one week prior to and after the 8 week intervention in the researcher's laboratory at the Ohio State University with the exception of the activity monitors. The Untrained group will only perform gait assessments without use of the HWA. The same outcomes will be used from Aim 1 with addition of the Stanford Self-Efficacy for Measuring Chronic Disease 6-Item Scale (SSE)²⁷ questionnaire to measure participants' confidence in performing daily activities. The SSE has been found to have good reliability and validity in individuals with Parkinson's disease.²⁸ To determine changes in activity levels, all participants will wear activity monitors (e.g., Biosensics LEGSysTM and PAMSysTM system wearable accelerometers) to quantitatively measure physical activity (e.g., number of steps, time spent walking, gait parameters, number of falls) for 5 consecutive days and complete a diary recording their daily activities during weeks 1 and 8 of the intervention period. To monitor safety during the study period the participants will be asked to record any falls (i.e., an event which causes the person to rest inadvertently on the ground or floor) or other adverse events that occur in a diary. **Sample Size:** The primary outcome for Aim 1 is to compare gait velocity pre and post treatment. For Aim 1, we will use the 23 patients randomized to the treatment arm and will have at least 80% power to detect a difference of 0.61 standard deviations in gait velocity using a two-sided paired t-test with type I error rate of 0.05. The primary outcome for Aim 2 is the gait velocity at 8 weeks. For Aim 2, we will have at least 80% power with 18 evaluable patients per group to detect a difference of 0.96 standard deviations in gait velocity at week 8 using a two-sided t-test with type I error rate of 0.05. Assuming a loss to follow-up rate of 20%,

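### Activity monitors are worn only in weeks 1 and 8 of the intervention, so change in activity has no scheduled pre-intervention baseline and no rule for session walking

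*Combined protocol and SAP*

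**What the plan says.** Aim 2, Outcomes gives the purpose, "To determine changes in activity levels, all participants will wear activity monitors", and the timing, "for 5 consecutive days and complete a diary recording their daily activities during weeks 1 and 8 of the intervention period". The other Aim 2 assessments take place within a week either side of the intervention, in the laboratory "at the Ohio State University with the exception of the activity monitors". Whether that exception concerns the place only or the timing too, the monitor sentence sets its own timing, and both wears fall inside the intervention period.

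Aim 2, Intervention gives Trained participants who attain a safe gait "supervised home and community-based walking training wearing the HWA device 2 times per week for 45-60 minutes for 8 weeks", adding "Rest breaks will be allowed as needed". The Untrained group carries on with its usual activities.

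Specific Aim 2 hypothesises an improvement in "daily physical activity in the home and community in individuals with PD with and without the use of the device".

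Data Analysis fits the Aim 2 primary outcome with a regression on arm, Hoehn and Yahr stage and the pre-intervention gait velocity, and handles secondary outcomes in a similar way. It does not say what serves as baseline for activity. I take activity to be a secondary outcome because it is an Aim 2 outcome other than the primary. Nowhere does the text say whether monitors stay on during sessions, or whether session time is counted, removed or reported apart.

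**The concern.** A measure of change needs a starting value. Every other Aim 2 outcome has one from before the intervention; activity does not. If the primary model is carried over, the only earlier activity reading is the week-1 wear. That value may already contain supervised walking in one arm, and perhaps some early benefit. Adjusting for it is not the same as adjusting for a pre-randomisation or pre-treatment covariate.

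The second gap is the definition of the measure. Sessions take place in and around the home, where the monitors record, and only one arm has them. The hypothesis covers activity both with and without the device, so the plan needs two quantities and gives no rule for obtaining the second. At stake is the interpretation of one non-primary outcome: whether a difference means that people walk more in daily life, or that they attended sessions.

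**Working it through.** **Plan's own figure.** None is given for activity. The Aim 2 sample size concerns gait velocity: 18 evaluable per group at 0.96 SD gives 79.9% power by the noncentral t, against the stated 80%, and 18/(1 - 0.20) = 22.5, rounded up to 23. Nothing below changes it.

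**Inputs from the plan.** Two sessions a week of 45-60 minutes for 8 weeks; wears of 5 consecutive days in weeks 1 and 8; no sessions in the Untrained arm.

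**Assumptions, not in the plan.** Monitors are worn and register walking during sessions. All session time is net added walking, which is an upper limit because of rest breaks and displaced walking. Mean session load is the same in both wears. Week 1 enters the model with slope b.

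**Step 1: session time in one wear.**
- One session: 45/5 to 60/5 = 9-12 min/day.
- Two sessions: 90/5 to 120/5 = 18-24 min/day.
- If the two sessions fall on any two different days of the week with equal chance, there are 21 day-pairs: 10 put both in the wear, 10 put one and 1 puts none. The mean is (10 x 2 + 10 x 1)/21 = 10/7 sessions. Then m = 10/7 x 9 to 10/7 x 12 = 12.9-17.1 min/day.

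**Step 2: session walking left after adjusting for week 1.** With mean session loads m1 and m8 in the two wears, the arm difference contains m8 - b x m1. If m1 = m8 = m, this is (1 - b) x m.

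| b (assumed) | Uniform day-pairs, m = 12.9-17.1 | Both sessions in each wear, m = 18-24 |
|---|---|---|
| 0.5 | 6.4-8.6 | 9-12 |
| 0.9 | 1.3-1.7 | 1.8-2.4 |
| 1 (change score) | 0 | 0 |

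Units are min/day. The figures scale down with the share of session time that is net added walking: at b = 0.5 and a share of one half, 6.4-8.6 becomes 3.2-4.3.

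**Step 3: benefit already present in week 1.** If a fraction f of the true week-8 effect E is present in week 1, the adjusted estimate loses b x f x E. By the end of week 1 at most 2 of 16 sessions have occurred. If benefit accrues in proportion to sessions (assumed), f is at most 2/16 = 12.5%. The loss is then at most 0.5 x 12.5% = 6.25% of E at b = 0.5, 0.9 x 12.5% = 11.25% at b = 0.9, and 12.5% for a change score.

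**Step 4: net effect.** Relative to activity outside sessions, the error is (1 - b) x m - b x f x E, two terms of opposite sign. With f = 0.125 and m = 12.9-17.1, they balance at E = 6.43/0.0625 to 8.57/0.0625 = 103-137 min/day when b = 0.5, but at 1.29/0.1125 to 1.71/0.1125 = 11-15 min/day when b = 0.9. If monitors come off in sessions, m is 0 and only the negative term remains. The plan gives neither b nor E, nor the net share of session time, so the sign cannot be fixed.

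**Step 5: an unadjusted week-8 comparison.** It needs no baseline to be valid, because the arms are randomised. It estimates the difference in total activity, session walking included.

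**The case against.** The strongest reply has four parts.

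*Total activity is a legitimate effect.* This stands. Supervised walking is the intervention, and the hypothesis includes activity with the device. A reader might infer that the outcome is biased by 12.9-17.1 min/day. The documents do not support that: the figure belongs to an unadjusted week-8 contrast that no section prescribes, and it is an error only if activity outside sessions is the target.

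*A change from week 1 to week 8 is nearly free of the problem.* This stands in part. Session time cancels in a change score only if its mean load is equal in both weeks. A fitting visit in week 1, fewer rest breaks later or sessions missed by week 8 would break the balance systematically, so unequal load cannot be dismissed as noise.

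*The week-1 wear might precede the first session.* It might. The text does not give the order, and the study flowsheet (Figure 3) was not available to check. A reader might infer that week 1 is certainly contaminated; the text shows only that no wear is scheduled before the intervention period.

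*Materiality is unproven for one non-primary outcome of a preliminary-efficacy trial.* This stands as a limit on severity. No mean or SD for activity is given, so the minutes cannot be set against usual activity. The daily diary could also identify sessions, although no section gives it that use.

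**Conclusion.** The point holds as a gap in measurement timing and definition, not as a demonstrated bias of known size or direction. The text schedules no activity reading before the intervention, leaves the baseline covariate for activity unnamed, and gives no way to separate session walking from the rest. Under the model that Data Analysis points to, session walking leaves up to 6.4-8.6 min/day at b = 0.5 and 1.3-1.7 at b = 0.9 under uniform day-pairs, on the upper-limit assumptions listed in the working. The opposing loss is at most about 12.5% of the effect if benefit accrues by session.

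A reader might infer that the trial's main conclusion is at risk. It is not: gait velocity has a true pre-assessment, and its sample size is untouched. This is a cheap improvement, but it must be made before participants start, because a missed pre-intervention reading cannot be recovered.

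**What to change.** In Aim 2, Outcomes, move the first 5-day wear into the existing week-before-intervention window, ahead of the first training session, and keep the week-8 wear. In Data Analysis, name the pre-training wear as the baseline covariate for activity.

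Moving the wear is not enough alone. A pre-training baseline holds no session time (m1 = 0), so nothing offsets the week-8 sessions. State whether monitors stay on during sessions, flag week-8 sessions from the existing diary or a short therapist log, and report total activity and non-session activity as two measures with the same adjusted model. Together these address both parts of the hypothesis.

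Placing the wear before the Trained group's first device exposure at the pre-assessment, or before allocation is disclosed ("participants will know the intervention to which they have been assigned"), is optional. The shown harm does not require it, and it could need a separate hand-out of monitors.

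Cost: the devices, wear days and diaries stay the same. Monitors must be handed out early enough to leave five days before training, sessions need brief logging, and the week-1 on-treatment reading is lost.

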Procedures: Demographic information will be collected (i.e., age, sex, disease duration, Parkinson's medications, numbers of falls in past 6 months) and a neurologist with UPDRS motor rating certification will administer the Unified Parkinson Disease Rating Scale (UPDRS) Part III –Motor Scale²³ to assess motor impairments and determine the Hoehn and Yahr stage. A researcher who is blinded to the participants' group allocation and trained on relevant assessments will perform all outcome assessments. Assessments will be collected with participants in the ON phase at around one hour after taking their usual Parkinson's medications. *The primary outcome measure, gait velocity, will be used to validate the effectiveness of the HWA to improve gait parameters for both Aim 1 and 2.* Gait velocity (e.g., walking speed) correlates with functional ability and has been linked to clinically meaningful changes in quality of life and in home and community walking behavior.²⁴ **Aim 1:** Only participants randomized to the Trained group (n=23) will complete this part of the study to eliminate exposure of the Untrained group to the HWA device. Gait assessments will be conducted first during unassisted walking followed by HWA-assisted (i.e., wearing the HWA device) walking, with rest breaks allowed between tests. Prior to HWA-assisted walking, the researcher will select the appropriate sized HWA device, assist the participants to correctly don the device, and adjust the HWA device settings to maximize the participants' safety while walking. The PIs are experts in application and use of the HWA device (preliminary data and unshown pilot studies). Initial device settings will be symmetrical flexion and extension assist bilaterally. The research therapist will make adjustments as needed based on the response to the symmetrical assist setting. If the therapist is unable to adjust the HWA to provide a safe gait pattern the testing will be ended and the device removed. Safe gait is defined as one that results in no increase in incidence of

[figure not shown]

Figure 2. Components of the HWA Device

stumbles and/or balance loss during HWA-assisted walking as compared to unassisted walking.

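### Does Aim 1 need a missing-pair rule and a lower stated power because assisted tests can be ended when no safe gait is reached?

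*Combined protocol and SAP*

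**What the plan says.** All references are to the combined protocol and SAP.

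- **Sample Size:** the Aim 1 claim is "we will use the 23 patients randomized to the treatment arm and will have at least 80% power", at 0.61 standard deviations, with a two-sided paired t-test at 0.05. The loss allowance, "Assuming a loss to follow-up rate of 20" percent, takes 18 evaluable patients to 23 enrolled per group and is stated for Aim 2.
- **Procedures, Aim 1:** unassisted walking comes first. The device is then fitted and adjusted: "Prior to HWA-assisted walking, the researcher will select the appropriate sized HWA device". A rule covers the case where the therapist proves "unable to adjust the HWA to provide a safe gait pattern the testing will be ended and the device removed". By the plan's definition, a gait counts as safe when there is no rise in "stumbles and/or balance loss during HWA-assisted walking as compared to unassisted walking".
- **Outcomes, Aim 1:** velocity is the mean of three walkway passes after one practice pass. Safety is measured as "gait safety using counts of observed episodes of stumbles and/or loss of balance".
- **Intervention, Aim 2:** the home fitting has the same kind of rule: "If the therapist is unable to adjust the HWA to provide a safe gait pattern, the session will be ended and the device removed".
- **Data Analysis:** Aim 1 has a paired t-test for velocity and unspecified paired methods for secondary outcomes. Intention to treat, per-protocol analysis and multiple imputation appear in the Aim 2 text.
- **Interim Monitoring:** safe-gait failures are counted after 10 treated patients complete the study. An acceptable rate of 20% is assumed and described as an estimate without preliminary data. The manufacturer reports that all eligible participants in earlier device studies could use it safely.
- **Project Objectives:** "It will also examine feasibility and safety of HWA usage in the PD population".

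**The concern.** Three things seem not to fit together.

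First, the Aim 1 power uses every patient in the Trained arm, while the procedures provide for ending an assisted test. A patient without an assisted velocity cannot contribute to a paired t-test, and the only loss allowance covers 8-week follow-up in Aim 2. If pairs are lost, a null velocity result has less power than stated.

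Second, no section names the Aim 1 analysis set or says how an ended test is treated. The velocity result could then describe only patients who attained a safe gait, without saying so.

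Third, the retention rule and the safety outcome use the same events. If stumbles are compared only among completers, patients who stumbled more with the device have been removed, and the comparison leans towards showing no increase. Safety is a stated objective, and the only planned evaluation of the failure rate is the interim check. A misleadingly reassuring stumble comparison would therefore matter.

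**Working it through.** **1. The plan's own power.** Inputs from Sample Size: n = 23, difference 0.61 SD, paired t-test, two-sided 0.05. I read the SD as that of the paired difference, because this reproduces the claim.

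Power = P(|T| > t crit), where T is noncentral t with n − 1 degrees of freedom and noncentrality 0.61 × √n.

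- n = 23: noncentrality 0.61 × √23 = 2.925, critical value 2.074 on 22 df, power **79.8%**.
- The difference detectable with exactly 80% power is 0.611 SD, which rounds to the stated 0.61.

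The figure reproduces.

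**2. Power if pairs are lost.**

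| Complete pairs | Power at 0.61 SD | Detectable at 80% (SD) |
|---|---|---|
| 23 | 79.8% | 0.611 |
| 22 | 77.9% | 0.626 |
| 20 | 73.5% | 0.660 |
| 18 | 68.4% | 0.701 |

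If each patient fails independently with probability f, average power is the sum over k of P(K = k) × power(k), with K ~ Binomial(23, 1 − f). The rates are assumptions.

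| f | Average power | Loss from 79.8% |
|---|---|---|
| 0% | 79.8% | 0 |
| 2% | 78.9% | 0.9 points |
| 5% | 77.5% | 2.3 points |
| 10% | 74.9% | 4.9 points |
| 20% | 69.2% | 10.6 points |

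The only experience cited in the documents supports the 0% row. The 20% row uses a figure chosen for a stopping rule.

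**3. Dependence on the SD scale.** If 0.61 were in SDs of velocity itself, the standardised paired difference would be 0.61 / √(2(1 − ρ)), where ρ is the within-patient correlation, which the documents do not give. With 18 pairs:

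- ρ = 0.5: 0.61, power 68.4%
- ρ = 0.7: 0.61 / √0.6 = 0.788, power 88%
- ρ = 0.8: 0.61 / √0.4 = 0.964, power 97%

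So the shortfall depends on this reading as well as on the failure rate.

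**4. Stumble selection.** The event rates are assumptions; the documents give none. The model has independent Poisson counts on walks of equal length and no therapist adjustment. A patient is kept if the assisted count used for the safe-gait judgement does not exceed the unassisted count. The retained difference is the mean assisted minus unassisted count among patients kept. Only rates that imply less than 20% failure are shown.

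| Mean unassisted / assisted | True difference | Implied failure | Retained, judged on a separate fitting walk | Retained, judged on the tested walk |
|---|---|---|---|---|
| 0.1 / 0.1 | 0 | 8.7% | −0.009 | −0.100 |
| 0.2 / 0.2 | 0 | 15.1% | −0.032 | −0.197 |
| 0.05 / 0.1 | +0.05 | 9.1% | +0.045 | −0.050 |
| 0.1 / 0.2 | +0.10 | 16.6% | +0.082 | −0.099 |

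On the fitting-walk reading the shift is between 0.05 − 0.045 = 0.005 and 0.032 stumbles per walk, and a true increase still shows as an increase. On the tested-walk reading the sign can reverse. Procedures places selection, fitting and adjustment of the device before assisted walking, which favours the first reading. Both columns also assume a completers-only comparison, which the plan does not state.

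**The case for a change.** The best case for a change is that power has no margin: 79.8% reaches 80% only by rounding, and one lost pair takes it to 77.9%. The protocol itself foresees failures and builds a stopping review around them. Deciding after the data are seen which ended tests count is what pre-specification should prevent. Even no failures in 23 would leave an exact 95% upper limit of 14.8%, so the failure rate deserves a final estimate. The cost would be a few sentences and no added patients.

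Part of this stands. No section defines the Aim 1 set or the handling of an ended test, and Interim Monitoring does not say whether failure at the pre-assessment, at the home fitting, or at either is counted. A completers-only stumble comparison would not be sound evidence of safety.

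The rest is conditional. The power statement already gives its condition, the 23 patients, for a single session where 8-week attrition does not apply. An ended test need not lose the primary outcome: velocity needs only short walkway passes, testing also includes a six-minute walk, and the order of tests is not given. The large stumble distortions need the less likely reading, assumed event rates and no therapist adjustment, although a test ends only when adjustment has failed.

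**Conclusion.** No change to the plan follows. The Aim 1 power is correct as stated, 79.8% for 23 complete pairs, taking 0.61 as SDs of the paired difference. The possible shortfall, about 2 points at 5% failure and 11 at 20%, rests on failure rates that the documents do not support with data. The stumble bias rests on a restriction that the plan does not impose; on the favoured reading it is about 0.03 stumbles per walk or less at the assumed rates.

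The unconditional part is a missing detail. A paired t-test uses patients with both measurements, so an analyst would take Trained patients with both velocities, state how many tests were ended, and confine the velocity conclusion to those who attained a safe gait. Failures are already counted for the interim review, and feasibility and safety are a stated objective, so giving the final failure proportion beside the stumble counts is ordinary reporting. No stated number or rule has been shown to give a wrong result.
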